# 6 DEMOGRAPHICS AND OTHER BASELINE CHARACTERISTICS

Description of the analysis of demographic and baseline characteristics of the participants is presented in this section. In listings, data will be presented typically sorted by participant number within each genotype group.

## 6.1 Demographics

All demographic characteristics obtained during the Screening Period will be summarized by genotype group and overall for the SS. This summary will include age (in years), sex (male), weight (kg), height (cm), body mass index (BMI in kg/m^2), race (Asian), ethnicity (Not Hispanic or Latino), ethnic subgroup (Japan) and CYP2C19 genotype.

The summary of age will include descriptive statistics and categorical summaries, the latter based on requirements for clinicaltrials.gov reporting ( $\leq 18$ , 19 to  $< 65$ , and  $\geq 65$  years) and the European Union Drug Regulating Authorities Clinical Trials (EudraCT) reporting ( $< 18$ , 18 to  $< 65$ , 65 to  $< 85$ , and  $\geq 85$  years).

A by-participant listing of demographic characteristics as well as the date of birth will be presented for the ES.

## **6.2 Other Baseline characteristics**

Lifestyle information (alcohol use, tobacco use, caffeinated beverage uses and illicit drug use) will be summarized by genotype group and overall for the SS and will be listed for the ES.

## **6.3 Medical history and concomitant diseases**

Medical history will be listed and summarized (in an incidence table) for the SS for all participants, by MedDRA system organ class (SOC) and preferred term (PT). The reported term will be included in the listing. The summary will include the number and percentage of participants and will be sorted alphabetically by SOC and by descending incidence of PT within each SOC, based on the 'All Participants' column.

Procedure history will be listed separately by the procedure reported term based on the SS. Concomitant medical procedures will be provided as a by-participant listing based on the reported term for SS.

## **6.4 Prior and concomitant medications**

Prior and concomitant medications will be listed for SS, respectively, by WHODD Anatomical Main Group (Level 1), Pharmacological Subgroup (Level 3) and PT.

Tabulations will be presented for prior and concomitant medications separately where prior medications will be summarized by genotype and concomitant medications will be summarized by treatment period and genotype. Prior medications which continued into the treatment period will also be classified as concomitant and will be included in both summaries. The reported term will be included in the listing.

All tabulations will be sorted alphabetically by Level 1 term, alphabetical Level 3 term within Level 1 and decreasing frequency of PT in the 'All Participants' column.

### **6.4.1 Prior medication definition**

Prior medications include any medications that started prior to date of the first dose of PSL.

### **6.4.2 Concomitant medication definition**

Concomitant medications are medications taken after the first dose of PSL and/or the SFU Period. Concomitant medications will be attributed to the treatment period in which they start. Thus, any medication taken on Day 1 through Day 5 will be attributed to the Single-Dose Period; any medications taken after the first dose of PSL on Day 6 through Day 14 (including SFU) will be attributed to the Multiple-Dose Period.

If a medication starts prior to PSL administration and stopped after the first PSL administration or stopped during the Single-Dose Period, then that medication will be classified as both prior and concomitant for Single-Dose Period only. If a medication starts prior to PSL administration and is stopped during the Multiple-Dose Period, then that medication will be classified as prior and concomitant for both Single and Multiple-Dose Periods.

Any medications with missing dates and/or times will be handled as described in Section 4.2.1 in order to classify them as prior or concomitant.

## 7 MEASUREMENTS OF TREATMENT COMPLIANCE

Administration of PSL will be performed under the supervision of the Investigator (or designee) and the Investigator (or designee) will check the study participant's hands and the oral cavity immediately after dosing to confirm ingestion of the study medication. Compliance will be monitored by drug accountability and by drug assay for PSL (using the drug concentration in the blood/plasma). Compliance with the study medication is defined as consumption by the study participant that confirms 100% with the planned dosage.

Drug administration/consumption will be recorded and any discrepancies with the dosing regimen will be explained. Dosing deviations will be included in the listing of IPDs where applicable.

No formal calculations of compliance will be presented as all study medication is administered on site.

## 8 EFFICACY ANALYSES

Not applicable.

## 9 PHARMACOKINETICS

The calculation of the PK parameters of PSL and its metabolites [REDACTED] will be performed by the Quantitative Clinical Development Department, PAREXEL.

Pharmacokinetic concentrations and PK parameters will be summarized by treatment period (Single-dose and Multiple-dose) and genotype group (EM, IM and PM) using the PK-PPS and listed by treatment period, genotype and study participant using the SS. Figures of summaries will be based on the PK-PPS and figures of individual concentrations will be based on the SS.

Pharmacokinetic parameters of PSL and its metabolites will be calculated using the actual blood sampling times.

The primary plasma PK parameters for PSL include:

- Single-dose:  $C_{max}$ ,  $AUC_{(0-t)}$ ,  $AUC$ ,  $t_{1/2}$ , and  $t_{max}$
- Multiple-dose:  $C_{max,ss}$ ,  $AUC_{\tau}$ ,  $t_{1/2}$ , and  $t_{max,ss}$

The other plasma PK parameters for PSL include:

- Single-dose:  $C_{max,bw}$ ,  $AUC_{(0-t),bw}$ ,  $AUC_{,bw}$ ,  $AUC_{(0-12)}$  and  $CL/F$
- Multiple-dose:  $CL_{ss}/F$ ,  $C_{max,ss,bw}$ ,  $AUC_{\tau,bw}$ ,  $R_{AUC}$ ,  $R_{Cmax}$ , and  $LF$

The other plasma PK parameters for PSL metabolites include:

- Single-dose:  $C_{max}$ ,  $AUC_{(0-t)}$ ,  $AUC$ ,  $t_{1/2}$ ,  $t_{max}$ ,  $C_{max,bw}$ ,  $AUC_{(0-t),bw}$ ,  $AUC_{,bw}$ ,  $AUC_{(0-12)}$  and  $m/p$  based on  $C_{max}$  and  $AUC$

- Multiple-dose:  $C_{\max,ss}$ ,  $AUC_{\tau}$ ,  $t_{1/2}$ ,  $t_{\max,ss}$ ,  $C_{\max,ss,bw}$ ,  $AUC_{\tau,bw}$ , m/p based on  $C_{\max,ss}$  and  $AUC_{\tau}$ ,  $R_{AUC}$ ,  $R_{C\max}$ , and  $R_{m/p}$  based on AUC

In addition, the PK parameters of PSL and its metabolites in urine after single and multiple-dose include:  $A_e$ ,  $f_e$ ,  $CL_r$  and  $CL_{form}$  (for PSL metabolites only).

## 9.1 Descriptive figures, Summaries and Listings

Individual plasma and urine concentrations of PSL will be listed separately by treatment period and genotype and will include the actual and nominal sampling times and the deviation between them. All deviations will be calculated relative to the first dose (single-dose) or the last morning dose (multiple-dose) of study medication. Any samples that are obtained outside the tolerance window permitted at the specified time point will be discussed at the DEM and any possible exclusion from analysis will be documented accordingly.

The plasma concentration and the PK parameters (plasma and urine) of PSL and its metabolites will be summarized by treatment period, genotype and nominal sampling times using descriptive statistics (number of available observations [n], arithmetic mean, median, SD, minimum, maximum, geometric mean, geometric CV and 95% CI for the geometric mean [assuming lognormally distributed data]). Values below the LLOQ will be reported with a clear sign (flag variable in the dataset) indicating that they were below the LLOQ.

The amount of urinary excretion of PSL (mg) per time interval after oral administration of PSL will be summarized by treatment period (SD: Day 1-5; MD: Day 10) and genotype using descriptive statistics.

Individual participant plasma concentration-time profiles of PSL and its metabolites will be displayed graphically overlaid on the same plot by treatment period in linear and semi-logarithmic scale.

Combined individual (spaghetti) plots for PSL and its metabolites will be displayed by treatment period and genotype with all participants overlaid on the same plot (linear and semi-logarithmic scale).

Geometric mean profiles of plasma concentrations for PSL and its metabolites over time will be presented, with genotype overlaid on the same plot, in both linear and semi-logarithmic scale. For the linear scale plot only, the lower and upper 95% confidence interval (CI) for the geometric mean will be displayed.

All plasma concentration figures will include the LLOQ on the semi-logarithmic scale plots and will be based on scheduled times.

The following PK parameters of PSL and its metabolites will be graphically displayed (scatter plot, box plot) by genotype:

- Single-dose: PSL and metabolites:  $C_{\max}$ ,  $AUC_{(0-t)}$ ,  $AUC$ ,  $C_{\max,bw}$ ,  $AUC_{(0-t),bw}$ ,  $AUC_{,bw}$ ,  $CL/F$ ,  $A_e$ ,  $f_e$  and  $CL_r$ ; PSL metabolites:  $CL_{form}$  and m/p based on AUC
- Multiple-dose: PSL and metabolites:  $C_{\max,ss}$ ,  $AUC_{\tau}$ ,  $C_{\max,ss,bw}$ ,  $AUC_{\tau,bw}$ ,  $CL_{ss}/F$ ,  $A_e$ ,  $f_e$ ,  $CL_r$  and  $R_{AUC}$ ; PSL: LF; PSL metabolites:  $CL_{form}$ , m/p based on AUC and  $R_{m/p}$  based on AUC

## 9.2 Statistical analysis of pharmacokinetics variables

The following PK parameters of PSL and its metabolites will be compared between genotype groups using analysis of variance (ANOVA) on the log-transformed parameters:

- Single-dose: PSL and metabolites:  $C_{max}$ ,  $AUC_{(0-t)}$ ,  $AUC$ ,  $C_{max,bw}$ ,  $AUC_{(0-t),bw}$ ,  $AUC_{,bw}$ ,  $CL/F$ ,  $A_e$ ,  $f_e$  and  $CL_r$ ; PSL metabolites:  $CL_{form}$  and  $m/p$  based on  $AUC$
- Multiple-dose: PSL and metabolites:  $C_{max,ss}$ ,  $AUC_{\tau}$ ,  $C_{max,ss,bw}$ ,  $AUC_{\tau,bw}$ ,  $CL_{ss}/F$ ,  $A_e$ ,  $f_e$ ,  $CL_{\tau}$  and  $R_{AUC}$ ; PSL:  $LF$ ; PSL metabolites:  $CL_{form}$ ,  $m/p$  based on  $AUC$  and  $R_{m/p}$  based on  $AUC$

Point estimates for the ratio of geometric means and the respective 2 sided 90% CIs will be computed using the least squares means and the root mean squares of error, based on of the log-transformed data with subsequent exponential transformation.

The 3 comparisons of interest are the following (in sequential ordering):

- EM versus PM
- IM versus PM
- EM versus IM

The comparison “EM versus PM” will be firstly evaluated and then the 2 other comparisons against IMs will be performed only if the comparison EM versus PM is nonequivalent.

Interpretation of results will be performed by comparing the 90% CI interval of geometric mean ratio with the acceptance range of 50% to 200%.

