## 9.4 Planned pharmacokinetic analysis

Pharmacokinetic parameters of PSL and its metabolites (██████████ and ██████████ in plasma ( $C_{max}$ ,  $t_{max}$ ,  $AUC_{(0-t)}$ ,  $AUC$ ,  $t_{1/2}$ ,  $CL/F$ ,  $C_{max,ss}$ ,  $t_{max,ss}$ ,  $AUC_{\tau}$ , and  $CL_{ss}/F$ ) will be estimated using noncompartmental analysis with Pharsight Phoenix® WinNonlin® v6.3 (or higher) software. Other PK parameters of PSL and its metabolites in plasma or urine will be derived with SAS v9.4 (or higher). For calculation of the plasma PK parameters, the actual blood sampling time points will be used in order to determine the PK parameters. The calculation of metabolite to parent ratio (m/p), based on  $C_{max}$  and  $AUC$  will be described in the SAP.

All PK analyses will be performed using the PK-PPS. Distribution of the CYP2C19 genotypes will be presented. The individual plasma concentration of PSL and its metabolites will be summarized by genotype group and nominal sampling time, and PK parameters of PSL and its metabolites will be summarized by genotype group using descriptive statistics (number of observations (n), geometric mean, lower and upper 95% confidence interval (CI), geometric CV, arithmetic mean, standard deviation, CV, median, minimum, and maximum) and graphical displays.

The following PK parameters of PSL and its metabolites between genotype groups will be graphically displayed (scatter plot, box plot) and compared using analysis of variance on the log-transformed parameters and estimation of the geometric ratio of PK parameters between genotype groups with their 90% CI will be provided for:

- Single-dose: PSL and metabolites:  $C_{max}$ ,  $AUC_{(0-t)}$ ,  $AUC$ ,  $C_{max,bw}$ ,  $AUC_{(0-t),bw}$ ,  $AUC_{,bw}$ ,  $A_e$ ,  $f_e$  and  $CL_r$ ; PSL metabolites:  $CL_{form}$ .
- Multiple-dose: PSL and metabolites:  $C_{max,ss}$ ,  $AUC_{\tau}$ ,  $C_{max,ss,bw}$ ,  $AUC_{\tau,bw}$ ,  $CL_{ss}/F$ ,  $A_e$ ,  $f_e$ ,  $CL_r$ ; PSL metabolites:  $CL_{form}$ .

The 3 comparisons of interest are the following (in sequential ordering):

- EM versus PM.
- Intermediate metabolizer (IM) versus PM.
- EM versus IM.

The comparison “EM versus PM” will be firstly evaluated and then the 2 other comparisons against IMs only if the comparison EM versus PM is nonequivalent.

Interpretation of results will be performed by comparing the 90% CI interval of geometric mean ratio with the acceptance range of 50% to 200%.

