## 2 PROTOCOL SUMMARY

### 2.1 Objectives and endpoints

Objectives	Endpoints
Primary	
To evaluate the plasma PK of PSL in CYP2C19 genotyped healthy male Japanese study participants (extensive, intermediate, and poor metabolizers)	

• Single dose: <math>C_{max}</math>, <math>AUC_{(0-t)}</math>, <math>AUC</math>, <math>t_{1/2}</math> and <math>t_{max}</math>

• Multiple-dose: <math>C_{max,ss}</math>, <math>AUC_{\tau}</math>, <math>t_{1/2}</math> and <math>t_{max,ss}</math>

Secondary	
To evaluate the safety and tolerability of PSL in healthy male Japanese study participants	Incidence of TEAEs
Other	

Objectives	Endpoints
To evaluate the plasma PK of PSL and its major metabolites [REDACTED] in CYP2C19 genotyped healthy male Japanese study participants (extensive, intermediate, and poor metabolizers)	
For PSL:
 

Single-dose: <math>C_{max,bw}</math>, <math>AUC_{(0-t),bw}</math>, <math>AUC_{bw}</math> <math>AUC_{(0-12)}</math> and <math>CL/F</math>

Multiple-dose: <math>CL_{ss}/F</math>, <math>C_{max,ss,bw}</math>, <math>AUC_{\tau,bw}</math>, accumulation ratios based on <math>AUC</math> and <math>C_{max}</math> (<math>R_{AUC}</math> and <math>R_{Cmax}</math>) and linearity factor (LF)

 
For PSL metabolites:
 

Single-dose: <math>C_{max}</math>, <math>AUC_{(0-t)}</math>, <math>AUC_{\tau}</math>, <math>t_{1/2}</math>, <math>t_{max}</math>, <math>C_{max,bw}</math>, <math>AUC_{(0-t),bw}</math>, <math>AUC_{bw}</math>, <math>AUC_{(0-12)}</math> and metabolite to parent ratios (m/p) based on <math>C_{max}</math> and <math>AUC</math>

Multiple-dose: <math>C_{max,ss}</math>, <math>AUC_{\tau}</math>, <math>t_{1/2}</math>, <math>t_{max,ss}</math>, <math>C_{max,ss,bw}</math>, <math>AUC_{\tau,bw}</math>, m/p based on <math>C_{max,ss}</math> and <math>AUC_{\tau}</math>, <math>R_{Cmax}</math>, <math>R_{AUC}</math> and accumulation ratio of m/p based on <math>AUC</math> (<math>R_{m/p}</math>)

To evaluate the urine PK of PSL and its major metabolites in CYP2C19 genotyped healthy male Japanese study participants (extensive, intermediate, and poor metabolizers)	
For PSL and its metabolites: Single and Multiple-dose: <math>A_e</math>, <math>f_e</math>, <math>CL_r</math>
 
Additional PK parameters of PSL metabolites (desmethyl and carboxy acid) in urine (<math>CL_{form}</math>)

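### Should CL/F and CLss/F be compared between genotypes for the metabolites, when only padsevonil is dosed?

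*SAP*

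**What the plan says.** Two sets of lists differ on the analyte.

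**Listed for PSL and its metabolites**

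- SAP 9.2, genotype ANOVA, single dose: "Single-dose: PSL and metabolites: $C_{max}$ , $AUC_{(0-t)}$ , $AUC$ , $C_{max,bw}$ , $AUC_{(0-t),bw}$ , $AUC_{,bw}$ , $CL/F".
- SAP 9.2, genotype ANOVA, multiple dose: "Multiple-dose: PSL and metabolites: $C_{max,ss}$ , $AUC_{\tau}$ , $C_{max,ss,bw}$ , $AUC_{\tau,bw}$ , $CL_{ss}/F".
- SAP 9.1, scatter and box plots, repeats this placement: "Single-dose: PSL and metabolites: $C_{\max}$ , $AUC_{(0-t)}$ , $AUC$ , $C_{\max,bw}$ , $AUC_{(0-t),bw}$ , $AUC_{,bw}$ , $CL/F". Its multiple-dose list does the same for CLss/F.
- Protocol 9.4, in the sentence on noncompartmental estimation for PSL and its metabolites: "CL/F$ , $C_{max,ss}$ , $t_{max,ss}$ , $AUC_{\tau}$ , and $CL_{ss}/F$ ) will be estimated using noncompartmental analysis". The protocol's multiple-dose comparison list also carries CLss/F for both analytes; its single-dose comparison list has no CL/F.

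**Listed for PSL only**

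- SAP 2.1, PSL entries: "AUC_{(0-12)} and CL/F" for the single dose and "Multiple-dose: CL_{ss}/F , C_{max,ss,bw" for multiple dosing. The metabolite entries contain neither.
- SAP 9, PSL list: "Multiple-dose: $CL_{ss}/F$ , $C_{max,ss,bw}$ , $AUC_{\tau,bw}$ , $R_{AUC}$ , $R_{Cmax}$ , and $LF". CL/F is in the single-dose PSL list just above it. The metabolite lists have neither.
- Protocol Table 3-1 gives CLss/F for PSL only and does not list CL/F as an endpoint.

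SAP 9.3 gives no formula for CL/F or CLss/F for any analyte, although it does give molecular-weight-adjusted metabolite formulas for fe and CLform. SAP 4.2.1 refers the noncompartmental work to a sponsor user guide that is not among the documents.

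**The concern.** Apparent clearance is normally dose divided by AUC. Only PSL is dosed, so for a metabolite that quotient equals metabolite clearance divided by (F x the fraction of PSL converted). It has the units of a clearance but depends on formation as well as elimination. In a study of whether CYP2C19 genotype alters PSL metabolism, formation is what may differ between groups. A genotype ratio with a 90% CI, reported under a clearance label, could be read as a change in metabolite elimination that never took place.

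The analyte labels in SAP 9.1 and 9.2 are otherwise used with care. The linearity factor, for instance, is set apart for the parent: "PSL: LF; PSL metabolites". That makes the placement of CL/F and CLss/F look like a slip. A programmer also meets one list asking for a metabolite parameter and another that does not name it.

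**Working it through.** **1. How much output is involved.** Counting the SAP 9.2 comparisons for one metabolite:

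- Single dose: 10 parameters shared with PSL, plus CLform and m/p = 12.
- Multiple dose: 9 shared with PSL, plus CLform, m/p and Rm/p = 12.
- Total 24, of which CL/F and CLss/F are 2.

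**2. What those two comparisons contain.** Inputs:

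- Scheduled doses (SAP 3.6): 200 mg on Day 1 and 200 mg on the morning of Day 10, the two profiled doses, for all three genotype groups.
- Assumed definition: CL/F = dose/AUC and CLss/F = dose/AUCtau.

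On the log scale on which the ANOVA is run,

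log(dose/AUC) = log(200) - log(AUC).

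The first term is the same constant for everyone, and so is any molecular-weight conversion. It drops out of every difference between groups. The residual mean square is unchanged, because reversing the sign of a variable does not alter its variance. The same participants contribute, because one quantity exists exactly when the other does. Therefore, for any pair of groups,

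- ratio for dose/AUC = 1 / (ratio for AUC);
- 90% limits for dose/AUC = 1/upper and 1/lower of the AUC limits.

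**3. A numerical check.** This uses the plan's CV of 39%, which is for PSL AUCtau and is borrowed here for a metabolite, and a metabolite AUCtau ratio EM versus PM of 1/1.3, chosen only to show the identity.

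- SD of log = sqrt(ln(1 + 0.39^2)) = 0.3763.
- 13 per group, three-group ANOVA: df = 39 - 3 = 36, t(0.95) = 1.688.
- CI factor = exp(1.688 x 0.3763 x sqrt(2/13)) = 1.283.

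| Parameter | EM/PM ratio | 90% CI |
|---|---|---|
| Metabolite AUCtau | 0.769 | 0.600 to 0.987 |
| Metabolite dose/AUCtau | 1.300 | 1.013 to 1.668 |

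1/0.769 = 1.300, 1/0.987 = 1.013, and 1/0.600 agrees with 1.668 up to rounding of the limit. The second row adds nothing to the first.

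**4. The verdict.** The acceptance range is 0.5 to 2.0, and 1/0.5 = 2.0. An interval for AUC lies inside the range exactly when its reciprocal does. The equivalence call is therefore always the same. So is the rule that the two comparisons involving IMs are made only if EM versus PM is nonequivalent: it opens or stays shut for dose/AUC exactly as for AUC.

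**5. What else is compared.** Metabolite AUC, AUCtau, CLform and m/p are in the same SAP 9.2 lists. A reader who wants to know whether formation differs by genotype has CLform for that purpose, with its formula in SAP 9.3.

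**The case for a change.** The strongest case for acting is that the documents contradict themselves, the label invites a wrong reading, and the cure is a list edit that loses no information precisely because the output is redundant. The study is meant to inform interaction potential and genotype-based dosing, so a quantity misread as metabolite elimination is not wholly harmless. SAP 3.9 also does not mention the CL/F and m/p comparisons that SAP 9.2 adds to those in Protocol 9.4.

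Part of this stands. The placement is inconsistent, and a metabolite CL/F should not be read as metabolite elimination. The rest carries less weight:

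- The dependence on formation is no special defect of dose/AUC. Metabolite AUC depends on formation and elimination in the same way, and comparing it by genotype is uncontroversial. Any worked example of a misleading metabolite CL/F is a metabolite AUC ratio turned upside down.
- The suffix /F already marks the quantity as apparent.
- Much of the mismatch is omission from endpoint lists that are not exhaustive. Protocol 9.4 estimates CL/F although Table 3-1 does not name it. SAP 9 introduces its metabolite parameters with wording that does not claim completeness. For CLss/F, SAP 9.2 simply follows the comparison list in Protocol 9.4.
- SAP 3.9 records PK parameters newly added to the set. m/p is already a protocol endpoint and CL/F is already in the protocol's estimation sentence, so neither was new in that sense.
- The documents do not show which list was intended. Restricting the two parameters to PSL, or keeping a defined apparent version for the metabolites, would be equally consistent with the text. No estimate or conclusion differs between the two.

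**Conclusion.** This is a clerical inconsistency, and correcting it would not change any result. It affects 2 of 24 comparisons per metabolite and the matching plots. All concern endpoints that the plan classes as other. Each is the reciprocal of a comparison the report will contain anyway, with the same equivalence verdict. The primary PSL parameters, the PSL genotype comparisons, the 50% to 200% decisions and the sample size are untouched. Whichever list a programmer follows, the informative metabolite results are the same, and a pharmacokineticist writing the report would recognise a metabolite CL/F as an apparent quantity.

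This rests on two assumptions: that CL/F and CLss/F mean dose over AUC and dose over AUCtau, and that everyone analysed received the scheduled 200 mg at the two profiled doses. The first is the usual definition, though SAP 9.3 does not state it. The second fits the design: doses are given by site staff, dose changes are barred except for safety (Protocol 6.6), and participants with important deviations affecting the PK parameters are left out of the PK per-protocol set.

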## 9.3 Derivations of pharmacokinetic parameters

- AUC will be calculated as  $AUC = AUC_{(0-t)} + C_{last}/\lambda_z$ , where  $C_{last}$  is the last quantifiable plasma concentration and  $\lambda_z$  is the apparent terminal elimination rate constant.
- $AUC_{(0-t)}$  will be calculated using the linear-up log-down trapezoidal rule. If single data points for plasma concentrations are missing, the parameter will be derived by interpolating with regard to the 2 neighboring non-missing concentrations.
- $t_{1/2}$  will be calculated as  $\ln 2/\lambda_z$  where a simple linear regression (slope =  $-\lambda_z$ ) of natural log ( $\ln$ ) concentration vs time for data points in the terminal phase of the concentration-time curve.
- Metabolite to parent ratio ( $m/p$ ) based on  $C_{max}$  will be calculated using  $C_{max}$  of metabolite divided by  $C_{max}$  of parent (PSL) and  $C_{max,ss}$  of metabolite divided by  $C_{max,ss}$  of parent for single and multiple dose respectively.
- Metabolite to parent ratio ( $m/p$ ) based on  $AUC$  will be calculated using  $AUC$  of metabolite divided by  $AUC$  of parent and  $AUC_{\tau}$  of metabolite divided by  $AUC_{\tau}$  of parent for single and multiple dose respectively.
- Body weight (BW) normalized parameters (ie,  $C_{max,bw}$ ,  $AUC_{(0-t),bw}$ ,  $AUC_{,bw}$ ,  $C_{max,ss,bw}$ , and  $AUC_{\tau,bw}$ ) will be calculated using the following formula where BW is measured on Day -1:

$$\text{Parameter}_{bw} = \text{Parameter} \times \frac{BW}{70}$$

- $CL_r$  will be calculated as  $A_e/AUC$  and  $A_e/AUC_\tau$  for single and multiple dosing respectively.
- $f_e$  will be calculated as  $A_e/\text{Dose}$  for PSL and as  $(A_e \text{ of metabolite}/\text{Dose}) \times (\text{molecular weight (MW) parent}/\text{MW metabolite})$  where the MW of PSL is 432.8, the MW of metabolite [REDACTED] is 419, the MW of metabolite [REDACTED].
- $CL_{form}$  will be calculated as  $(A_e \text{ of metabolite}/\text{AUC of parent}) \times (\text{MW parent}/\text{MW metabolite})$  for single-dose period and as  $(A_e \text{ of metabolite}/\text{AUC}_\tau \text{ of parent}) \times (\text{MW parent}/\text{MW metabolite})$  for multiple-dose period.
- Accumulation ratio of  $C_{max}$  ( $RC_{max}$ ) will be calculated using  $C_{max,ss}$  following multiple dosing divided by  $C_{max}$  following a single dose for PSL and its metabolites.
- Accumulation ratio of  $AUC$  ( $RAUC$ ) will be calculated using  $AUC_\tau$  following multiple dosing divided by  $AUC_{(0-12)}$  following a single dose for PSL and its metabolites.
- Accumulation ratio of m/p based on  $AUC$  ( $Rm/p$ ) will be calculated using m/p [based on  $AUC$ ] following multiple dosing divided by m/p [based on  $AUC$ ] following a single dose.
- Linearity factor will be calculated using  $AUC_\tau$  following multiple dosing divided by  $AUC$  following a single dose for PSL.

